### **Duration of response (DoR)**

Duration of response (DoR) is defined as the time from when the first response (CR, CRi, PR, nPR, VGPR, PR-L, and MR) was achieved until the earlier of the first documentation of definitive disease progression or death from any cause. If patients do not have disease progression or death, they will be censored following the same rules as for PFS. Only patients with response of CR, CRi, PR, nPR, VGPR, PR-L, or MR will be included in the analysis for DoR.

DoR (months) = ([date of first documentation of definitive PD or death from any cause] - [date of first response] + 1)/30.4375.

Percentages for the number of events/censorings of DoR will be calculated based on the number of responders.

Median DoR along with the two-sided 95% CI will be estimated using Kaplan-Meier method. The 95% CI for the median will be calculated using a log-log transformation based on

HMPL-523

Brookmeyer and Crowley (Brookmeyer, R., & Crowley, J. 1982) method. Kaplan-Meier curve will be plotted by dose level in Stage 1 and by the malignancy type in Stage 2.

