### **Progression free survival (PFS)**

PFS is defined as the time (in months) from the date of first study medication to the earliest date of disease progression or death due to any reason whichever occurs first.

HMPL-523

PFS (months) = ([date of progression or death or censoring] - [date of first dose of study medication] + 1)/30.4375.

A patient is deemed to be censored according to the rules specified in **Error! Reference source not found.** below.

Error! Reference source not found.: **Progression-Free Survival Censoring Rules**

#	Situation	Date of Progression or Censoring	Outcome	Event/Censor reason
1	Death (without previously documented progressive disease [PD]) within two evaluable tumor assessments [a] from last evaluable tumor assessment or first dose (if no post-baseline tumor assessment)	Date of death	Event	Death
2	Death (without previously documented PD) after two or more consecutive missed/non-evaluable tumor assessments [a] from last evaluable tumor assessment or first dose (if no post-baseline tumor assessment)	Date of last evaluable tumor assessment or date of first dose (if no post-baseline tumor assessment)	Censored	Death after two or more consecutive missed or NE tumor assessments
3	Progression within two evaluable tumor assessments [a] from last evaluable tumor assessment or first dose (if no post-baseline tumor assessment before PD)	Date of progression	Event	Disease Progression
4	Progression after two or more consecutive missed/non-evaluable tumor assessments [a] from last evaluable tumor assessment or first dose (if no post-baseline tumor assessment before PD)	Date of last evaluable tumor assessment or date of first dose (if no post-baseline tumor assessment before PD)	Censored	Progression after two or more consecutive missed or NE tumor assessments
5	Progression after new anti-cancer treatment	Date of last evaluable tumor assessment before new anti-cancer treatment or date of first dose (if no post-baseline tumor assessment before new anti-cancer)	Censored	Progression after new anti-cancer therapy
6	No baseline tumor evaluable assessment and alive	Date of first dose	Censored	No baseline assessment
7	No post-baseline tumor evaluable assessment and alive	Date of first dose	Censored	No post-baseline assessment

HMPL-523

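### Read literally, the DoR rule lets through as late events some PDs and deaths that the PFS table censors, so one responder can be censored in PFS and a later event in DoR

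*SAP*

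**What the plan says.** SAP section 16.1.1 runs DoR from first response "until the earlier of the first documentation of definitive disease progression or death from any cause". It then adds: "If patients do not have disease progression or death, they will be censored following the same rules as for PFS". The formula is "DoR (months) = ([date of first documentation of definitive PD or death from any cause] - [date of first response] + 1)/30.4375".

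The PFS formula in the same section does provide for censoring: "PFS (months) = ([date of progression or death or censoring] - [date of first dose of study medication] + 1)/30.4375". Three rows of the PFS censoring table concern patients who do have an event but are censored at an earlier evaluable scan:

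- Row 2: "Death (without previously documented PD) after two or more consecutive missed/non-evaluable tumor assessments"
- Row 4: "Progression after two or more consecutive missed/non-evaluable tumor assessments"
- Row 5: "Progression after new anti-cancer treatment"

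Note [b] below the table also censors PFS when new therapy starts before PD or death.

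Protocol sections 4.8.4 and 7.3.5 define DoR and name the Kaplan-Meier method. Neither gives a censoring rule for DoR.

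**The concern.** The DoR sentence first selects patients by whether they have PD or death, and only those with neither go to the PFS rules. Rows 2, 4 and 5 apply only to patients who have one or the other, so the condition shuts them out. The same holds for note [b] where PD or death follows new therapy. For responders, that leaves in practice rows 8 and 9.

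A responder with PD after a long unscanned interval is then censored in PFS at the last evaluable scan but is a DoR event at the later PD date. DoR can include months without a scan or time on another therapy. The PFS and DoR tables would show different event counts for the same patients, with no stated reason. Two programmers could also build different DoR datasets from this text.

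Stage 2 DoR is reported by malignancy type, and the cohorts in protocol Table 2 are small: HL 25, PTCL 9, CLL post-BTK 7, and 0 to 2 in each of the others. Responders will be no more numerous, so a single reclassified patient may be visible in the curve.

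**Working it through.** **The plan's own windows.** The SAP text under the PFS table defines two consecutive missed assessments from the 8-week and 12-week schedule, allowing 7 days early and 7 days late:

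- last scan before Day 120: 2×8×7 + 14 = 126 days
- last scan Day 120 to 176: 7×8 + 7×12 + 14 = 154 days
- last scan from Day 176: 2×12×7 + 14 = 182 days
- first cut-off: 7×16 + 7 + 1 = Day 120

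All four agree with the SAP.

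**Missed scans (row 4).** Hypothetical responder on nominal scan days, with first dose on Day 1: first response Day 57 (week 8), last evaluable scan Day 113 (week 16), weeks 24 and 36 missed, PD Day 337 (week 48).

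- Gap: 337 − 113 = 224 days, above the 126-day limit, so row 4 applies.
- PFS: censored at 113/30.4375 = 3.71 months.
- DoR as written: event at (337 − 57 + 1)/30.4375 = 9.23 months.
- DoR under the PFS rules: censored at (113 − 57 + 1)/30.4375 = 1.87 months.

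This PD falls within 12 months of first dose, so scheduled tumor follow-up could record it.

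**New therapy (row 5).** Response Day 57, last scan Day 169, new therapy Day 180, PD Day 253. The gap is 253 − 169 = 84 days, below the 154-day limit, so only the new-therapy rule applies.

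- PFS: censored at 169/30.4375 = 5.55 months.
- DoR as written: event at (253 − 57 + 1)/30.4375 = 6.47 months.
- DoR under the PFS rules: censored at (169 − 57 + 1)/30.4375 = 3.71 months.

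**Effect on the curve.** Take eight invented responders, all responding on Day 57. Five progress on schedule on Days 113, 169, 253, 337 and 421, and one is event-free at Day 505. Two have PD after missed scans: last scan Day 113 with PD Day 337, and last scan Day 169 with PD Day 421 (gap 252 days, above 154).

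| | DoR as written | DoR under PFS rules |
|---|---|---|
| Events | 7 | 5 |
| Kaplan-Meier estimate just after 6.47 months | 7/8 × 6/7 × 5/6 = 0.625 | 7/8 × 5/6 × 3/4 = 0.547 |
| Median | 9.23 months | 9.23 months |

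Here the event count and the curve change while the median does not. A late event in place of an early censoring adds both follow-up time and an event, so the effect on the median depends on the data.

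**The case against.** The strongest reply is that the sponsor meant every PFS row to apply. PFS is also defined without qualification as progression or death, and its table then decides which events count. On that view the DoR sentence is shorthand for patients with no qualifying event. The missing censoring date proves little, since taken literally it would leave no date even for patients whom the text expressly censors. This reading is possible, and the formula alone looks like a drafting omission. But it is not what the conditional sentence says, and nothing else in the SAP or protocol supplies it.

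PD after new therapy should also be uncommon, because scheduled tumor assessment stops when new anti-cancer therapy starts (protocol section 5.6.12). That stands, and it makes missed scans the main route. Deaths after new therapy remain possible. Their capture is limited too: once the adverse-event reporting period ends, protocol section 6.7 asks for notification only of deaths thought related to HMPL-523.

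The analysis is descriptive, with no test or decision rule on DoR, and per-patient listings of DoR and of PFS censoring reasons would expose a mismatch. That limits the harm but does not tell the programmer which dataset to build.

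A reader might infer two stronger points that the documents do not support:

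- **That DoR is a primary endpoint of Stage 2.** The objective is preliminary efficacy; protocol section 4.8.4 lists ORR, DoR, TTR and PFS without ranking them, and the only outcome labelled primary is DLT incidence.
- **That a DoR longer than the same patient's PFS is impossible.** It compares an event time with a censoring time. It shows two censoring conventions at work, not an impossible value. Counting PD or death despite missed scans or later therapy is a recognised choice, provided it is stated.

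**Conclusion.** The point holds on the wording. As written, rows 2, 4 and 5, and note [b] where PD or death follows new therapy, do not reach DoR, and the same PD or death can be censored in PFS and counted later in DoR. In the missed-scan example the DoR result changes from censored at 1.87 months to an event at 9.23 months.

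The examples are hypothetical and use nominal scan days. The documents give no count of responders with missed scans or new therapy, so neither the number affected nor the direction of any change in median DoR can be stated. The conclusion rests on reading the condition in the DoR sentence literally. Even if the broader reading was intended, the text needs to say so. This should be corrected before database lock. It is a defect of consistency between endpoints, and it does not show that reported DoR will be materially biased.

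**What to change.** Replace the DoR censoring sentence with a rule for every responder: DoR event status, and the event or censoring date, are those of the PFS analysis, using all rows of the PFS table and note [b]. Change the formula to DoR (months) = ([date of PD or death or censoring] − [date of first response] + 1)/30.4375.

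First reconcile the PFS rules on death after new therapy. Row 1 makes a death within the assessment window an event without mentioning new therapy, while note [b] censors it. Otherwise the conflict passes into DoR.

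Reusing the PFS date should not produce a censoring date before first response: the response scan is itself evaluable, and best overall response stops counting at new therapy.

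If the sponsor does want late PD and deaths to count in DoR but not in PFS, the SAP should state that and justify it.

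The cost is a few lines of SAP text and reuse of the PFS status and date variables. No new data are needed.

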4.8.4 Efficacy Outcome Measures

- ORR is defined as the proportion of patients who have a BOR of CR or PR. The BOR in an individual patient is the best response recorded from the start of treatment until progression or the date of any further anticancer therapy, whichever comes first.
- DoR is defined as the time from when the first response (CR or PR) was achieved until the first documentation of definitive disease progression or death from any cause, whichever occurs first.
- TTR is defined as the time from the date of the first dose of the study drug to first response (CR or PR).
- PFS is defined as the time from the date of the first dose of the study drug until the date of disease progression or death due to any cause.

Efficacy in different subgroups will be evaluated according to specified guidelines/criteria:

- Chronic lymphocytic leukemia: the modified International Workshop on CLL guideline (modified International Workshop on Chronic Lymphocytic Leukemia [IWCLL] 2008, see [Appendix 4](#))
- WM/LPL: consensus of international workshops on WM (IWWM-7 Consensus, see [Appendix 5](#))
- Lymphomas other than CLL or WM/LPL: Lugano Response Criteria for Hodgkin and NHL ([Cheson et al 2014](#), see [Appendix 6](#))

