## 2. INTRODUCTION

This study is a two-stage, open-label, multicenter Phase 1 study to evaluate the safety, Pharmacokinetics (PK), and preliminary efficacy of HMPL-523 in patients with relapsed or refractory lymphoma who have exhausted approved therapy options. The study consists of two stages. Stage 1 is a dose escalation phase, in which a modified 3+3 design is applied for the dose escalation and to determinate the maximum tolerated dose (MTD) / recommended Phase II dose (RP2D). Stage 2 is a dose expansion stage, in which the safety, tolerability, PK, and preliminary efficacy of HMPL-523 at MTD/RP2D will be further evaluated in patients with relapsed, refractory, or resistant NHL.

The purpose of this Statistical Analysis Plan (SAP) is to provide a description of the statistical methods and conventions to be implemented in the presentation and analysis of efficacy and safety data from study 2018-523-00US1. This document is based on Protocol Amendment 5 dated 14Jun2024. It describes the data to be summarized and analyzed, including specifics of the statistical analyses to be performed. If circumstances arise during the study such that more appropriate analytic procedures become available, the SAP may be revised. This SAP supersedes the statistical considerations identified in the protocol; where considerations are substantially different, they will be identified. Any revisions to the SAP will be made and finalized prior to the final Database Lock (DBL), and any deviations from the SAP will be documented in the final Clinical Study Report (CSR).

The PK and pharmacodynamics analyses will be described in a separate analysis plan. All statistical analyses except for PK specific analyses will be performed by IQVIA Biostatistics.

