### **Objective response rate (ORR)**

ORR is defined as the proportion of patients who have BOR with CR, CRi, nPR or PR for CLL patients; the proportion of patients who have BOR with CR, VGPR, PR or MR for WM patients; the proportion of patients who have BOR with CR or PR for patients with disease type other than CLL and WM.

The definition of neo-OR is similar with that of classical OR except that partial response with lymphocytosis (PR-L) is also included for CLL.

The estimated ORR and 95% Clopper-Pearson CI (Clopper, C. J., & Pearson, E. S. 1934) will be presented by dose level for Stage 1 and by the malignancy type for Stage 1 and Stage 2.

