### **Time to response (TTR)**

TTR is defined as the time from the first dose of study treatment to the first occurrence of CR, CRi, PR, nPR, VGPR, PR-L, or MR. Only patient with response of CR, Cri, PR, nPR, VGPR, PR-L, or MR will be included in the analysis for TTR.

$TTR = ([\text{date of first response}] - [\text{date of first dose of study medication}] + 1) / 30.4375$ . Median TTR along with the two-sided 95% CI will be estimated using Kaplan-Meier method. The 95% CI for the median will be calculated using a log-log transformation based on Brookmeyer and Crowley (Brookmeyer, R., & Crowley, J. 1982) method. Kaplan-Meier curve will be plotted by dose level in Stage 1 and by the malignancy type in Stage 2.

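### In CLL the SAP computes DoR and TTR on a wider responder set (adding PR-L) than the ORR it reports; in WM it counts minor response where the protocol counts only CR or PR

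*SAP*

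**What the plan says.** **Protocol.** Section 4.8.4 defines ORR, DoR and TTR from CR or PR. For DoR: "DoR is defined as the time from when the first response (CR or PR) was achieved until the first documentation". The same section sends CLL to the modified IWCLL criteria in Appendix 4 and WM/LPL to Appendix 5. Appendix 4 defines a classical ORR (CR, CRi, nPR, PR) and a neo-ORR that adds PR-L.

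**SAP 16.1.1, ORR.** For CLL: "ORR is defined as the proportion of patients who have BOR with CR, CRi, nPR or PR for CLL patients". For WM: "the proportion of patients who have BOR with CR, VGPR, PR or MR for WM patients". Other diseases use CR or PR. One further sentence defines neo-OR for CLL by adding PR-L. The reporting sentence that follows names ORR only.

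**SAP 16.1.1, DoR and TTR.** One pooled list serves all diseases. For DoR: "Only patients with response of CR, CRi, PR, nPR, VGPR, PR-L, or MR will be included in the analysis for DoR". For TTR: "Only patient with response of CR, Cri, PR, nPR, VGPR, PR-L, or MR will be included in the analysis for TTR". Neither paragraph mentions neo-OR. On the DoR table: "Percentages for the number of events/censorings of DoR will be calculated based on the number of responders".

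**SAP Section 2.** The SAP supersedes the protocol's statistical considerations, and "where considerations are substantially different, they will be identified".

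**The concern.** ORR, DoR and TTR are linked. A reader takes the responders counted in ORR to be the patients whose response times are then described. In CLL that link is broken, because PR-L patients supply durations and response times without being in the reported rate.

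The start date matters too. A CLL patient who passes through PR-L to PR is an ORR responder, but both clocks are set at the earlier PR-L date.

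In WM the three SAP endpoints agree with one another, but they are not the protocol's endpoint, because MR has been added.

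Preliminary efficacy is the primary objective of Stage 2, so these definitions shape the main efficacy tables for the CLL and WM/LPL cohorts.

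**Working it through.** **1. Responder sets side by side.** The pooled DoR/TTR list is restricted here to the categories that SAP 16.1.1 allows for each disease under best overall response.

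| Endpoint | Protocol 4.8.4 | SAP, CLL | SAP, WM | SAP, other |
|---|---|---|---|---|
| ORR | CR, PR | CR, CRi, nPR, PR | CR, VGPR, PR, MR | CR, PR |
| Neo-OR | (Appendix 4, CLL: adds PR-L) | CR, CRi, nPR, PR, PR-L | none | none |
| DoR, TTR | from first CR or PR | CR, CRi, nPR, PR, PR-L | CR, VGPR, PR, MR | CR, PR |

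The only mismatch inside the SAP is PR-L in CLL. MR differs between SAP and protocol, not between SAP endpoints.

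**2. Do the extra categories fit within CR or PR?** Appendix 4 treats nPR as a PR, places CRi in classical ORR, and keeps PR-L out of classical ORR. In Appendix 5, PR needs an IgM fall of at least 50% and VGPR at least 90%. MR is a fall of 25% to under 50%, below the PR threshold. CRi, nPR and VGPR can therefore be read as CR or PR; PR-L and MR cannot without a stated decision.

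**3. Shift in the clocks.** The SAP divides days by 30.4375. Scans are every 8 weeks to week 24, then every 12 weeks. If PR-L is seen at one scheduled scan and PR at the next:
- 8-week interval: 56/30.4375 = 1.84 months
- 12-week interval: 84/30.4375 = 2.76 months

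TTR is shorter and DoR longer by that amount than under the protocol's first CR or PR.

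**4. The one PR-L breakdown in the documents.** Protocol 2.2.4.4 (the sponsor's China study, CLL/SLL expansion cohort, N = 16) gives 1 CR, 4 PR and 4 PR-L, with a stated ORR of 56.3% (95% CI 29.9% to 80.2%). The Clopper-Pearson limits are the 0.025 quantile of Beta(x, n−x+1) and the 0.975 quantile of Beta(x+1, n−x).
- With PR-L: (1+4+4)/16 = 9/16 = 56.3% (29.9 to 80.2), which reproduces the stated figure.
- Without PR-L: (1+4)/16 = 5/16 = 31.3% (11.0 to 58.7).
- Under this SAP's lists, 9 patients would enter DoR against 5 classical responders. Four of the 9 (44%) would be PR-L only. If the denominator were classical responders, event and censoring percentages would sum to 9/5 = 180%.
- Under neo-OR both counts are 9 and the mismatch disappears.

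This is an illustration from another study. Its 16 patients include 4 with SLL, and this SAP assesses SLL by Lugano criteria, which have no PR-L category.

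**5. Scope here (Protocol Table 2, Amendment 5 column).** CLL 1 + CLL post-BTK 7 = 8; WM/LPL 1. The column sums to 25+1+7+2+2+1+1+9+0 = 48, so 48 − 9 = 39 Stage 2 patients are unaffected. The 8 is an upper bound, since the eligibility criteria describe these cohorts as CLL/SLL. If all 8 are CLL and response-evaluable, each PR-L-only patient moves a pooled CLL rate by 1/8 = 12.5 points.

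**6. Chance that it arises.** With an assumed PR-L-only rate p among 8 patients, P(at least one) = 1 − (1−p)^8.

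| p (assumed) | Expected number | P(at least one) |
|---|---|---|
| 10% | 0.8 | 57% |
| 25% (the China 4/16) | 2.0 | 90% |
| 40% | 3.2 | 98% |

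For the single WM/LPL patient, a best response of MR gives 1/1 under the SAP and 0/1 under the protocol.

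**The case against.** The strongest reply is that the DoR/TTR list is not arbitrary. It is neo-OR for CLL, the SAP's own ORR for WM, and CR or PR elsewhere. Neo-OR is prespecified in the SAP text and in Appendix 4 of both documents, and under it a PR-L patient is a responder whose clock properly starts at PR-L. The China study already reported its ORR with PR-L included and DoR for those responders. The SAP also tabulates PR-L and MR as separate best-response categories, so a reader could rebuild any rate. The protocol itself points to disease-specific criteria.

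Much of this stands. A reader might infer that durations are being reported for non-responders in general. The documents do not support that. MR patients are responders in the SAP's WM ORR, and PR-L patients are responders under neo-OR; they fall outside only the classical ORR and the protocol's CR-or-PR wording. Nor is the 44% from the China data an estimate for this trial.

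It does not remove the defect. The SAP's reporting sentence names ORR alone, DoR and TTR never invoke neo-OR, and the number of responders is left undefined. The best-response table can restore a rate but not a Kaplan-Meier curve or a start date. Protocol 2.2.4.5 cites the PR-L-inclusive 56.3% as part of the rationale for the post-BTK cohort, so which ORR is shown affects comparison with that figure.

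**Conclusion.** The point holds in limited form. In CLL, the SAP as written gives DoR and TTR sets and start dates that match neither its reported ORR nor Protocol 4.8.4, and the DoR percentage denominator cannot be programmed without a choice that the SAP does not make. In WM, the SAP is internally consistent but adds MR to the protocol endpoint.

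A reader might also infer that the sponsor broke its undertaking to identify departures. That goes too far: the main SAP's modification history is redacted, so all that can be said is that no readable text identifies either change.

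The size is small: at most 8 CLL and 1 WM/LPL of 48 Stage 2 patients, plus CLL and WM patients in Stage 1, whose number is not given. The study is single-arm and descriptive, with sample size based on detecting adverse events, so no test or sample size changes. The conclusion rests on reading CRi, nPR and VGPR as falling within CR or PR. How often PR-L occurs here is unknown, and the 10% to 40% range is an assumption. The wording should be corrected before database lock.

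**What to change.** In SAP 16.1.1:
- Compute CLL DoR and TTR on the classical ORR responders, from the first CR, CRi, nPR or PR.
- State that neo-ORR will be reported for CLL, with neo-DoR and neo-TTR (adding PR-L, starting at PR-L) beside it.
- Define the DoR percentage denominator as the classical or the neo responders, to match each analysis.
- Report WM ORR as CR + VGPR + PR, give any MR-inclusive rate a separate label, and align WM DoR and TTR with the first definition.
- Add a short list of any remaining departures from Protocol 4.8.4, as Section 2 of the SAP undertakes.

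The cost is SAP wording and a few extra table rows. No new data are needed, because response categories are already recorded separately.
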